Primary: The primary outcome, measures whether a child has had a dental extraction under General Anaesthetic two years after referral as indicated in electronic patient records (recorded through HES data or through CDS patient records).

Secondary: The secondary outcomes to be considered in this project include:

- Waiting time until first appointment
- Number of sessions of treatment
- Whether a child was successfully seen and treated. For this outcome success is defined as treatment completed by a dentist that results in a child being referred back to their own dentist or discharged, pain free.
- The number of extractions and restorations as reported in NHS BSA data
- The courses of antibiotics taken during wait and treatment
- Participants referred back into the specialist pathway within two years of referral.
- Dental pain experienced by a child
- Participants views of their treatment and engagement with the dental profession (follow up of dental appointment) as indicated by the responses to the text message. Questions will include an adapted version of the NHS Friends and Family Test, questions on satisfaction, possible negative/adverse experiences, possible positive experiences, and an option for free text comments at the end of the survey.

Qualitative work will focus on two groups: (a) dental professionals (incl. triage, in-practice dental teams, CDS teams and referring practices) and (b) patients (incl. parents and children) accessing and using CFDPs.

(a) Dental teams' attitudes and beliefs regarding CFDP will be examined to better understand what worked well, what created barriers and look at how best to support implementation for such initiatives if they become routine practice.

In a qualitative approach, we will explore dental team beliefs, attitudes, and opinions regarding CFDPs and traditional pathways. To allow for the realist evaluation to take place, a combination of focus groups and one-to-one interviews will take place with the triage team and staff at CFDPs.

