Verbal consent will be obtained from participants through a verbal consent script prior to the commencement of any interview questions. Participants will be asked to clearly state their names in the audio recording following a comprehensive explanation of the study's objectives and the purpose of the interview, which would be read aloud individually by the research staff and provided to participants in a clear and concise language. Participants will be asked to confirm "Yes" or "No" to taking part in the interview with additional points will be clearly stated. Prior to soliciting consent, participants will undergo a confirmation of understanding to ensure comprehension of the study's aims and importance of their response. Only after this confirmation will verbal consent be sought for participation in the qualitative interview. Additionally, participants will be informed of their right to refuse participation or withdraw consent at any point during the interview process. The verbal consent process will be thoroughly documented, including the date of consent, and confirmation of the participant's agreement to participate. Alternatively, written consent can also be sought if requested by participants. Participants who consent to partake in the interview will be sent a hard copy of the consent form via email or post. Qualitative interviews will be recorded on a recording device. Information shared by consented participants will only be used for research purposes, Audio recordings will be pseudo anonymised with participant ID, and at a later stage in the study, the audio files will be renamed to "Parent 1" to destroy the link between the name and the participant ID. After data analysis is completed, data will be deleted and destroyed after two years Only approved transcription services will be used, audio recordings will be transferred from devices onto secure UoM storage as soon as possible following the interview and deleted from the audio recording device.

Cost effectiveness

Healthcare resource utilisation will be collected for those treated in both the Child Friendly Dental Practice and Specialist Paediatric Dental Service pathways.

- Dental resource use: treatments provided, prescriptions of antibiotics. Data collected from routine data NHS BSA and local clinical records

PANDA study - An evaluation of an alternative Dental Pathway V1.4 02/04/2024 IRAS 323977

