- Secondary care resource use: dental extractions under GA. Data collected from routine data: HES and CDS software
- Intervention resource use for CFDP pathway: additional costs paid to deliver the pathway (as outlined in the service level agreement) and additional costs in terms of setting up the pathways (providing training and resources/support for dentists. Data collected from CFDP providers and commissioners.

Unit costs will be attached to dental treatments via the dental treatment band and the associated Units of Dental Activity cost. Unit costs for prescribed antibiotics will be obtained from Prescriptive Cost Analysis data (21). Unit costs for secondary care resource use are sourced from the Healthcare Resource Group tariffs for tooth extractions(22).

Intervention costs will be attached data from CFDP providers and commissioners using salary costs from Unit Costs of Health and Social Care (23). The cost per patient for each pathway will be summarised and presented adjusted for inflation.

The health economics analysis will adopt a cost-consequences approach whereby the costs of each pathway will be presented separately but alongside relevant outcomes: 1) dental extractions under GA, 2) count of children who are successfully seen and treated in each pathway, 3) count of treatments performed (extractions, restorations), 4) mean wait time and 5) dental pain experienced by a child. Resource use and costs from the CFDP pathway will also be used in a budget impact analysis. Differences in outcomes will be generated from the quantitative analysis.

The analysis will take an NHS perspective with a 2 year time horizon. Longer term costs and outcomes will not be modelled due to the need for treatment being acute and focusing on child teeth. This approach will provide dental service commissioners with appropriate health economic data to inform future commissioning decisions related to CFDP.

VII. Monitoring of the study

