A steering group, will monitor this study at periodic intervals. This group will include the Principal Investigator, University of Manchester staff, lay member of the community (Public and Patient Involvement (PPI) to ensure that the study is being conducted according to Good Clinical Practice Guidelines. An Oversight Committee (chaired by [name]) will monitor and feedback to both the research group and NIHR. Further PPI - patient and public involvement - will be sought for various aspects of the study including visits to practices for recruitment opportunities and through organisations which work with parents and children (such as sure start) to gain relevant opinions on the study, for example both the questionnaire and leaflet will be given to parents to fill in to test before the study begins.

The research will be monitored by the Lead Investigator on a weekly basis and at key project milestones.

The study will be subject to the audit and monitoring regime of the University of Manchester.

VIII. Data handling

The data controller will be the University of Manchester. Data will be collected through

- Clinical examinations. Dentists at the CFDP or CDS will fill out a Case report form (CRF) including information on treatment, antibiotic use (see Appendix B) - pseudo anonymised
- Text message surveys. Participants will answer text message survey at baseline, 1 year and 2 years after consent (See Appendix B). Surveys through text message survey (Text messages will be sent to participants using SafeMessage. SafeMessage is operated by FDS Consultants who are an NHS Business Partner (ODS: 8J025) who have met the following regulatory and legislative requirements: Fully completed NHS

DSPT, CyberEssentials Plus, Data stored in HSCN servers within ISO27001 certified, UK only data centres, DCB0219 met, Clinical Safety Officer, Data Protection Officer and Calidcott Guardian. The system is regularly penetration tested and complies with all the requirements of NHS Digital for the safe storage of sensitive data under GDPR.)

Answers from text message survey will be transferred to csv and pseudo anonymised

- Routinely collected data. Following participants consent, data will be linked and collected to be used within the study. This data will come from but not limited to NHS BSA, NHS England, HES, clinical records from the Community Dental Service, GDP and CFDP and referral forms (See appendix B) this data will be pseudo anonymised.

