Appendix A – Gantt Chart

APPENDIX B – Data collection

Data collected through CDS

ID	Contract Number	Provider Name	Locality	Month of Submission to Dental Comm Team	Practice patient code	Pt Age (in years)	Patient Postcode	URN	Referring Practice Name	Referring GDP Name	Referring Practice Postcode	Number of courses of Antibiotics whilst waiting?

Date of Referral	Appt made? (Yes / No)	Reason no appt (Please select from the drop down)	Number of appts attended	Number of appts WNB	Bitewings taken?	Date of Initial Appointment	Number of decayed teeth needing treatment *at CDS	Outcome (please select from drop down)

Treatment Provided								Notes	Who carried out treatment	Previously seen at CFDP or other services after referral	GM central emergency system (Out of hours) Y/N
Number of Filling(s)	Number of Extraction(s)	Number of Stainless Steel Crowns (SSCs)	Number of Temp Fillings	Fluoride Varnish Application (Y/N)	Silver Diamine Fluoride (SDF) (Y/N)	Oral Health Improvement Advice Given (Y/N)	Antibiotics (Yes / No)				

Data collected through CFDP

ID	Contract Number	Provider Name	Locality	Month of Submission to Dental Comm Team	Practice patient code	Pt Age (in years)	Patient Postcode	URN	Referring Practice Name	Referring GDP Name	Referring Practice Postcode

Number of courses of Antibiotics whilst waiting?	Date of Referral	Appt made? (Yes / No)	Reason no appt (Please select from the drop down)	Date of Initial Appointment	Number of appts attended	Number of appts WNB	Bitewings taken?	Number of decayed teeth needing treatment
			Cannot contact					

Treatment Provided								Outcome (please select from drop down)	Notes	Who carried out treatment	GM central emergency system (Out of hours) Y/N	Patie
Number of Filling(s)	Number of Extraction(s)	Number of Stainless Steel Crowns (SSCs)	Number of Temp Fillings	Fluoride Varnish Application (Y/N)	Silver Diamine Fluoride (SDF) (Y/N)	Oral Health Improvement Advice Given (Y/N)	Antibiotics (Yes / No)					

NHS BSA data headings

Link	Flagged (linked or not linked data set 0 = not linked, 1 = linked)
PANDA_ID	PANDA ID (include if linked)
PATIENT_ID	Patient ID (random number generated by NHS BSA for each patient)
Age of Pt at every CoT	age of Pt at every CoT (will need to use DOB and treatment date)
GENDER	Gender
PT_LSOA	Lower Super Output Area of patient's home address at time of treatment

IMD	UoM will supply this as a post-code lookup. IMD against NEPU 2019 scores an
IMD rank	

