Indicate if following is requested (GA)	GA no GA
Previous dental history	free text
Main reason for referral	tick box
Teeth requested for treatment within referral	dental chart
Complexity score	tick box
Reason for referral	free text
Medical behaviour indicators	tick box
Patient anxiety question	5 questions on likert scale
radiograph included	yes no
Date of referral	date

Text message survey

	Text message Question	Potential response
1	Does your child have any pain in his/her mouth/teeth at the moment? Please reply: yes or no.	"Yes" / "No"
1a	If yes, how would he/she rate this pain from 1 (not too painful) to 10 (most painful pain ever)?	"1-10"
2	Has your child received any antibiotics for a dental problem recently for example, in the last year?	"Yes" / "No" / "Can't remember"
2a	If yes, do you remember how many days he/she was given and for how long did he/she take them? Just type your answer below.	Open text
3	In the last 3 months, has your child had any of the following problems: pain, difficult sleeping, problems eating/drinking?	"pain" / "sleeping" / "eating/drinking"
4	Overall, how was your experience of the service you attended for your child's dental treatment. Please reply: very good, good, neither good nor poor, poor, very poor?	"very good" / "good" / "neither" / "poor" / "very poor"
5	Did you feel the service your child attended for their dental treatment was appropriate for your child? Please reply: yes definitely, yes to some extent, no	"yes definitely" / "yes" / "no"
6	Would you recommend the service to family and friends? Please reply: yes, no, not sure	"Yes" / "No" / "Not sure"

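### The antibiotic outcome is a number of courses over wait and treatment, but the case report forms count courses only for the wait and record Yes/No for treatment

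*Protocol*

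**What the plan says.** The Outcomes section of the Protocol (under VI) lists as a secondary outcome "The courses of antibiotics taken during wait and treatment". It names no data source for it, although the entry for extractions and restorations does name NHS BSA data.

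Section VIII (Data handling) makes the case report form one source: "Dentists at the CFDP or CDS will fill out a Case report form (CRF) including information on treatment, antibiotic use".

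Appendix B shows the CDS and CFDP forms. Both have the column "Number of courses of Antibiotics whilst waiting", which is a count. In the treatment block both have "Antibiotics (Yes / No", which is a flag. In that same block, fillings, extractions, stainless steel crowns and temporary fillings are each entered as a number.

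The text message survey in Appendix B asks "Has your child received any antibiotics for a dental problem recently for example, in the last year", with Yes, No or Can't remember as answers. Those who say yes are then asked "do you remember how many days he/she was given and for how long did he/she take them".

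For the health economics, the Cost effectiveness section says: "Dental resource use: treatments provided, prescriptions of antibiotics. Data collected from routine data NHS BSA and local clinical records". It adds: "Unit costs for prescribed antibiotics will be obtained from Prescriptive Cost Analysis data".

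**The concern.** The outcome adds two periods in one unit, courses. The forms deliver that unit for the first period only. A child given three courses during treatment looks the same as a child given one, and a count plus a flag is not a number of courses.

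The outcome compares two pathways that may differ in how many appointments and how much time treatment takes. If repeat courses are more common in one pathway, the flag understates use more in that pathway. An analysis plan can choose between sources, but it cannot recover from the form a number that the form never asked for.

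**Working it through.** The protocol gives no figure for antibiotic use, so there is no stated number to reproduce. The check sets the outcome against each possible source and then illustrates the size of the loss.

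**Can each source give courses during wait and treatment?**

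| Source | Wait | Treatment |
|---|---|---|
| CDS and CFDP forms (Appendix B) | number of courses | Yes/No only |
| Text survey (Appendix B; sent at baseline, 1 year and 2 years after consent) | no course count; window not tied to the wait | no course count; window not tied to treatment |
| NHS BSA extract (Appendix B) | two antibiotic fields, neither described | same |
| Clinical records (section VIII) | may hold the number | may hold the number; linkage described following consent |

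On the forms: each also records the number of appointments attended, so one entry appears to cover several visits. On that reading a single Yes/No collapses repeat courses.

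On the BSA extract: it lists ANTIBIOTICS and ANTIBIOTICS_COUNT without descriptions. Where such pairs are described (radiographs, extractions), the plain field holds a quantity and the field ending in _COUNT is an indicator. By analogy ANTIBIOTICS may be a quantity, but the protocol does not say so. The contract types requested are GDS and PDS. CDS is not named, and the protocol does not say how CDS care is recorded in BSA data.

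On the unconsented children: the Sample size section supplements the CFDP group with them. For these children section VIII describes referral-system data, commissioner data and linkage with NHS England and NHS BSA. It describes no clinical-record access and no text survey for them.

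**How much could a Yes/No field miss?** Assume courses per child during treatment are Poisson with mean m. The flag records at most one course, so its expected value is 1 − exp(−m). The share of treatment-phase courses missed is 1 − [1 − exp(−m)]/m.

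| Assumed m | 1 − exp(−m) | Share of treatment-phase courses missed |
|---|---|---|
| 0.1 | 0.095 | 5% |
| 0.25 | 0.221 | 12% |
| 0.5 | 0.393 | 21% |
| 1.0 | 0.632 | 37% |

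The wait part is fully counted, so the share missed of the whole outcome is smaller. With an assumed mean of w courses during the wait it is [m − (1 − exp(−m))]/(w + m). If w = m, this is half the share in the table: for m = 0.5, (0.5 − 0.393)/(0.5 + 0.5) = 0.107, or about 11%.

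**The case against.** The strongest reply is that the form is not the only source. Section VIII lists linked clinical records and NHS BSA data, and ANTIBIOTICS may well be a quantity. A reader might infer from the form alone that the outcome cannot be derived at all. The documents do not support that, and this part of the reply stands. What they do show is that the form cannot give the count and that no other source is shown to give it for all children in both groups.

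A reader might also infer that the costing is spoiled. It is not directly affected, because antibiotic prescriptions for costing are assigned to NHS BSA data and local clinical records, not to the form.

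A third tempting step is to put a size on the bias between pathways. Assumed Poisson means of 0.5 and 1.0 would turn a true difference of 0.50 courses into 0.632 − 0.393 = 0.24. But those means have no basis in the protocol, and the figure concerns the treatment part only. The protocol's own rationale links repeat courses to the long wait, which is the period that is counted. If no child has more than one course during treatment, nothing is lost.

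It can also be said that the text survey serves the long-term question and was never named as the source for this outcome. That is fair. The survey is mentioned here only because it does not fill the gap.

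Finally, choosing among collected sources is often left to the analysis plan. That is true, but it does not cover a field that records the wrong unit when it is filled in.

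**Conclusion.** The point holds for the case report forms. They count antibiotic courses during the wait and record only any versus none during treatment, so they cannot yield the secondary outcome in its stated unit, and second or later treatment-phase courses are lost from them. The text survey gives no course count. NHS BSA data and clinical records may hold one, but the first is undescribed and of unclear coverage for CDS care, and access to the second is described only for consented children.

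The size of the loss cannot be computed from the documents. Under the Poisson illustration it ranges from about 5% to 37% of treatment-phase courses for means from 0.1 to 1.0, with the wait count unaffected. The reading also assumes that one form entry spans a child's treatment.

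This concerns one secondary outcome; the primary outcome and the sample size are untouched. It is still worth correcting, because the change is small and the lost count cannot be restored from the forms afterwards.

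**What to change.** - On both Appendix B forms, replace the Yes/No antibiotic field in the treatment block with the number of antibiotic courses from first appointment to discharge.
- In the Outcomes section, define the outcome as the wait count plus this count.
- For children already entered, take the treatment-phase number from clinical records where consent allows.
- For unconsented CFDP children, use a defined NHS BSA or commissioner count if one exists in both groups. State which field it is and what it holds.
- If no such count exists in both groups, analyse treatment-phase use as any versus none in both groups, and report it separately from the wait count.

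The cost is one changed column on each form, a sentence or two in the Outcomes section, and minor re-abstraction for children already entered. The fallback costs more in information: it gives up the combined number of courses, but it keeps the measure the same in both groups.

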Cases of tooth decay become more complex, and children are more likely to be referred into this system when the decay is severe or affects multiple teeth, the child suffers from dental anxiety, or the child is very young. Currently, General Dental Practitioners (GDPs, which we will refer to as High Street Dentists when describing a dentist who refers from their practice into the referral system) who feel unable to treat such complex cases may refer them on to a Specialist Paediatric Dentistry pathway, where they may be treated within one of two specialist settings: (Setting 1) to hospital (secondary care) or (Setting 2) to dentists with enhanced skills and specialist equipment and facilities (Community Dental Service) (7).

One solution to this crisis of children waiting, often in pain, for treatment is to increase capacity, however there are limits on being able to increase capacity within the existing specialised pathways, both within the hospital services and within the Community Dental Services. Hospital services have downward pressure from other paediatric specialties who also require specialised space and staff, and the Community Dental Service is intended to provide complex care for adults and children with additional needs, but is currently overwhelmed by otherwise healthy young children with extensive decay.

In late 2020, as a response to the increased pressure caused by Covid-19, a new model of enhanced primary care was piloted in Greater Manchester (GM), the Child Friendly Dental Practice (CFDP) Scheme. The aim was to provide timely access to dentists who have an interest in treating young children and who have received some additional training, access to a specialist-led peer support network and additional funding. The CFDPs have been developed around a prevention focused and evidence-based model of care with the aim of improving oral health outcomes. These include clinical techniques for treatment which are not typically used by High Street Dentists such as applying Silver Diamine Fluoride and placing preformed metal crowns using the 'Hall Technique' (8).

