While the pilot indicated promising results, with 50% of children being able to be seen within a CFDP, the long term impacts and health outcomes of the use of CFDP are unknown. There have also been concerns raised from some within the field that children treated within a CFDP may still require future intervention in a more specialist service, within a short period of time. If so, there would not be a reduction on the pressure seen on these services and the overall costs of this scheme would be higher than usual care. The proposed research is required to provide a robust, longitudinal evaluation of the CFDP pathway, building on the initial work from the pilots, which can strengthen the case for nationwide adoption if shown to be successful. Following a realist evaluation approach will also mean the research will provide evidence of what works, for whom and when. The project will provide evidence of long term outcomes (treatment required, pain, use of antibiotics) and a health economic evaluation which can be utilised by commissioners for future schemes. If a high proportion of children referred to specialist services can be treated at CFDPs, this model has the potential to improve access to care across the system. In particular, increased use of CFDPs could allow hospital/specialist services to focus on those in greater need. The implementation of an alternative pathway could allow those urgent cases, and cases for which a dental GA is unavoidable, such as medically compromised children and those with additional needs, to be seen sooner. It may also reduce the need for GA for some children if they are seen sooner than they would otherwise be seen along a traditional pathway.

Research objectives.

The aim of this research is to determine the performance of CFDP pathway compared to a traditional Specialist Paediatric Dental pathway on the longer term oral health and treatment outcomes for children referred to specialist care due to severe decay and the associated health economic costs.

Our primary and secondary research questions (and subsequent objectives/methods) are as follows:

Primary

- *Does treatment through a CFDP reduce treatment under General Anaesthetic when compared to the traditional pathway over a period of 2 years?*
 - Using GA data gained from Hospital Episode Statistics (HES)/Community Dental Service (CDS) records the team will assess the number of GAs carried out along each pathway for dental extraction.

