A referring dentist should chart all teeth in a referral indicating all teeth that are carious and which are symptomatic. When deciding triage outcome, if one or two teeth only are symptomatic (i.e., causing pain) and this could be managed by extraction/restoration, then the child would be suitable for management within CFDP. The child should attend the referring dentist for completion of treatment (shared care model).

Not suitable for management in CFDP:

Child who has developmental defects of permanent teeth requiring treatment

Child with three or more symptomatic carious teeth

Child with unrestorable teeth in three or four quadrants e.g., extractions indicated in three or four quadrants

Child who needs root canal treatment (RCT) in permanent teeth

Child with moderate to severe medical complexities

Child with moderate to severe behavioural complexities

VII. STUDY DESIGN Prospective, comparative, observational cohort study

VI: Planned interventions:

The exposed cohort will receive care following triage and treatment through the alternative pathway (treatment through the new CFDP).

The control cohort (non-exposed) will receive care following triage and treatment through the traditional pathway (treatment through the Specialist Paediatric Dental pathway).

Time scale (see appendix for more detailed time line)

Year 1 – 2023

Months Feb-March -Study set up

Months Feb-March -Ethics application

Months March – PPI development,

Months May -December (2024) – Recruitment

Months May - December (2024) – Data collection (CRF)

Months May – September – Observational data collection

Months May – March (2024) -text message survey

Months Nov – Dec – Data coding

Months August to October – Qualitative interviews

Year 2 – 2024

Months Jan -Feb – NHS BSA application

Months May-July – Text message survey

Months May – September – Observational data collection

Months August to October – Qualitative interviews

Months November to December -Qualitative analysis

Year 3 – 2025

Months March – April finalise NHS application

Months May – August -text message survey

Month June – August – NHS data retrieval (NHS BSA, CDS, clinical records, NHS digital, HES)

Month September – November – Data analysis

Month November -Jan – report write up

Year 3 – 2026

Month Jan – March -Dissemination

Outcomes

Proposed outcome measures

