Summary descriptive data will be reported by study arm and overall using tables of frequencies or means and standard deviations as appropriate to characterise the population and identify any imbalance between groups. The comparison of outcomes from the traditional specialist dental service route (control) compared to the intervention treatment under the alternative Child-Friendly Dental Practice will be assessed to determine if there are clinically meaningful and statistically significant differences in key outcomes. The primary outcome is receipt of GA for tooth extraction within two years of initial referral. Referral along both pathways may still result in the need for a GA for some children but a key metric will be to determine whether there

is a meaningful difference in the number of GAs per referral pathway. The primary outcome will be analysed using a mixed effects logistic regression model, accounting for the traditional specialist dental service route or alternative Child-Friendly Dental Practice, with random effects for centre. An adjusted logistic regression analysis additionally accounting for the age, deprivation, ethnicity, sex of the child along with the number of teeth requiring treatment at initial examination (through the CFDP or CDS) will also be undertaken. The analysis dataset will include all participants for whom there is follow-up data from the NHS BSA and the baseline covariates.

Analysis of secondary outcomes will be undertaken in a similar manner using covariate adjusted linear or logistic regression models as appropriate, we will include the modifying effect of deprivation

The health economics analysis will adopt a cost-consequences approach whereby the costs of each pathway will be presented separately but alongside relevant outcomes: 1) dental extractions under GA, 2) count of children who are successfully seen and treated in each pathway, 3) count of treatments performed (extractions, restorations), 4) mean wait time and 5) dental pain experienced by a child. Resource use and costs from the CFDP pathway will also be used in a budget impact analysis. Differences in outcomes will be generated from the quantitative analysis.

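### The secondary outcome of referral back into the specialist pathway is not the same event in the two arms, so comparing it between pathways is biased against the Child Friendly Dental Practices.

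*Protocol*

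**What the plan says.** - **Outcome.** Under Outcomes (Proposed outcome measures), the protocol lists as a secondary outcome "Participants referred back into the specialist pathway within two years of referral". The item is one line. It gives no definition by arm and no restriction to one arm.
- **What the specialist pathway is.** The Background in section I describes a Specialist Paediatric Dentistry pathway to which complex cases may be sent, "where they may be treated within one of two specialist settings": hospital and the CDS.
- **Where controls start.** Section VI (Planned interventions) states that "The control cohort (non-exposed) will receive care following triage and treatment through the traditional pathway", which it glosses as "treatment through the Specialist Paediatric Dental pathway". The sample size section names the control sites as CDS.
- **How a child leaves.** The outcome of being successfully seen and treated is defined as "treatment completed by a dentist that results in a child being referred back to their own dentist or discharged, pain free". Exit followed by a fresh referral is thus possible in either arm.
- **Analysis.** Section X states: "Analysis of secondary outcomes will be undertaken in a similar manner using covariate adjusted linear or logistic regression models as appropriate". It makes no exception for the referral-back item.
- **A related question.** The Research objectives in section I include a separate question, limited to the CFDPs, on the proportion and characteristics of children who need onward referral.

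**The concern.** A CFDP child whose needs exceed what the practice can provide is sent to the CDS or hospital. That child enters the specialist pathway and can be counted. A CDS child with the same need stays on at the CDS or moves to hospital. Both are inside the pathway already, so nothing is counted. The two arms share one route to an event, re-referral after discharge, but the CFDP arm has a second route that controls lack. Covariate adjustment cannot repair this, because the outcome itself is measured differently by arm.

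The item bears on a worry the protocol itself reports in its rationale: that "children treated within a CFDP may still require future intervention in a more specialist service, within a short period of time". The risks and benefits section says the study's results will decide whether the Greater Manchester scheme is kept, widened or stopped. A built-in excess on this outcome could be read as evidence for that worry when need is in fact the same in both arms.

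**Working it through.** **The plan's own figures.** The protocol gives no expected rate and no power for this outcome, so there is nothing to reproduce for it directly. The sample sizes used below are the protocol's. The 354 per group reproduces exactly for 25% against 15%, 90% power, two-sided 5%, with the two-proportion formula and continuity correction (335 without the correction). The protocol's alternative split is 460 CFDP and 292 CDS.

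**Which events count.**

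| Course after the initial referral | CFDP child | CDS child |
|---|---|---|
| Needs care beyond the first provider | Sent to CDS or hospital: enters the pathway, can count | Continues at CDS or moves to hospital: already in the pathway, does not count |
| Discharged, then referred again | Counts | Counts |

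**Model under equal need.** Let q be the proportion needing escalation beyond the first provider and r the proportion of the remainder who are re-referred after discharge. Both are set equal in the two arms.

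- CFDP event proportion: q + (1 − q)r
- CDS event proportion: (1 − q)r
- Difference: q + (1 − q)r − (1 − q)r = q

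So the spurious excess equals q, whatever r is. As an example, q = 10% and r = 5% give 0.10 + 0.90 × 0.05 = 14.5% for CFDP and 0.90 × 0.05 = 4.5% for CDS.

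**Chance of a false result against the CFDP.** This is an exact binomial enumeration of a two-sided 5% pooled z-test, counting only rejections in the direction of a CFDP excess, with 460 CFDP and 292 CDS children and no clustering or covariates. The values of q and r are assumptions; the protocol gives neither.

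| q | r | CFDP | CDS | Rejection against CFDP |
|---|---|---|---|---|
| 2% | 5% | 6.9% | 4.9% | 19% |
| 3% | 5% | 7.9% | 4.9% | 35% |
| 3% | 20% | 22.4% | 19.4% | 16% |
| 5% | 5% | 9.8% | 4.8% | 72% |
| 5% | 10% | 14.5% | 9.5% | 53% |
| 5% | 20% | 24.0% | 19.0% | 36% |
| 10% | 20% | 28.0% | 18.0% | 89% |
| 10% | 10% | 19.0% | 9.0% | 97% |
| 10% | 5% | 14.5% | 4.5% | 99.7% |

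The nominal one-sided level is 2.5%. With 354 per group the results are close: 20% at q = 2%, r = 5%, and 99.7% at q = 10%, r = 5%.

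**Another parameterisation.** Suppose 10% in each arm have further need and only a share s of it can be counted in the CDS arm. At 354 per group, rejection against the CFDP is 99% for s = 0.25, 72% for s = 0.5, 22% for s = 0.75, 7% for s = 0.9 and 2.5% for s = 1. Once the same event counts in both arms, the error returns to its nominal level.

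**A tempting repair that fails.** One could test CFDP to CDS or hospital against CDS to hospital. A need the CDS can meet is then an event for a CFDP child and not for an identical CDS child. If half of an equal need can be met at the CDS (an assumption), the 460 and 292 split gives 25% against 12.5% with 99% rejection, or 10% against 5% with 71%.

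**The case against.** The strongest objection is one of reading. The item speaks of being referred back, and the same list foresees children returning to their own dentist or being discharged. The CFDP-only research question uses a different term, onward referral. One can therefore read the secondary outcome as re-entry after discharge, which can happen in both arms. That reading is possible, but the text does not fix it. CFDP children were themselves referred for specialist care, so sending them on is also naturally described as a referral back. The CFDP-only question does not restrict the outcome item. A statistical analysis plan could settle the matter, but the protocol already ties the event to entering a pathway in which one arm starts.

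Other parts of the case against stand and limit the point:

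- A reader might infer that only CFDP children can score. The documents do not support that: a discharged control who is referred again meets the wording.
- A reader might infer that a false finding against the CFDP is near certain whatever its performance. That holds only for some assumed rates; others give 16% or 19%. The calculation also treats no CDS escalation as countable and ignores the adjusted models of section X.
- Extraction under general anaesthetic is captured in both arms by the primary outcome, so a control who moves to hospital for one is not lost there. Referral back is not among the five outcomes in the cost-consequences analysis.
- CFDP transfers into specialist care are a real measure of load on those services and worth reporting. They are simply not a like-for-like comparison with controls.

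**Conclusion.** The point holds as a difference in event definition between arms. As worded, and compared between pathways as section X provides, the outcome is biased against the CFDP when need for further care is equal. The excess equals the proportion needing escalation. The resulting false rejection rate ranges, over the rates tried, from under 20% (16% at q = 3%, r = 20%; 19% at q = 2%, r = 5%) to over 99% (q = 10%, r = 5%), against a nominal 2.5% in that direction.

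The direction follows from the protocol's own text, given the reading that transfer counts. The size rests on assumed rates, an unadjusted test and independent children. This is one secondary outcome, and the primary comparison is unaffected. It should be corrected because it addresses a question that commissioners care about and the correction is cheap.

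**What to change.** 1. For the between-arm comparison, define the item as a new referral through the referral system after the index course of treatment ends (discharge or return to own dentist), within two years of the initial referral. Apply one rule in both arms, whichever service the child is then sent to. State that a transfer between services does not itself end the index course.
2. Report transfer from CFDP to CDS or hospital as a CFDP-only proportion with a confidence interval, under the existing onward-referral question.
3. Report CDS-to-hospital transfer descriptively where records capture it. Do not test it against CFDP transfer.

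**Cost.** A change of outcome wording and two derived variables in place of one. The between-arm item will no longer count transfers during the index course. The sponsor should confirm two data points. First, the referral-system extract must hold later referrals of the same child. Second, transfers from CDS to hospital without a general anaesthetic may not be recorded: the HES and CDS linkage fields in Appendix B name only the anaesthetic, its referral date and its date, and the options of the CDS form's outcome field are not shown.
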